a: General objective

To assess the effect of coffee consumption on hunger, satiety, appetite-regulating hormones, and dietary intake in women with overweight or obesity.

b: Specific objectives

1. To describe the demographic, anthropometric, biochemical, and dietary characteristics of the study sample.
2. To compare the sensations of hunger and satiety at times $t=-30$ min, $t=0$ min, $t=30$ min, $t=60$ min, $t=90$, $t=120$, $t=150$ min and $t=180$ min between the two interventions: coffee and simple water.
3. To compare the serum levels of cholecystokinin and ghrelin at times $t=-30$ min, $t=0$ min and $t=180$ min between the two beverage interventions (coffee and simple water).
4. To compare the change ($t=180 - t=0$) in hunger and satiety sensations between the two beverage interventions (coffee and simple water).
5. To compare the change ($t=180 - t=0$) in cholecystokinin and ghrelin concentrations between the two interventions (coffee and simple water).

7. Hypothesis

Coffee consumption decreases hunger and ghrelin, increases satiety and cholecystokinin concentrations, and changes energy intake in women with overweight or obesity.

8. Methodological design

a. Type of study

Randomized crossover clinical trial.

b. Research location

Instituto de Nutrigenética y Nutrigenómica Traslacional (INNUGET) of the Centro Universitario de Ciencias de la Salud of the Universidad de Guadalajara.

c. Study period

The scientific literature review phase began in September 2020 and the study is expected to conclude in April of 2023.

d. Inclusion and non-inclusion criteria

Inclusion criteria

- Women between 20 and 40 years old
- Body mass index between 25 to 40 kg/m²
- Regular menstrual cycle of 25-32 days in the last 3 months
- Moderate coffee consumption (2 cups per day)
- Having the habit of eating breakfast

- Availability of time in the morning

Non-inclusion criteria

- Use of any type of contraceptives in the last three months
- Consumption of hypoglycemic, lipid-lowering, weight-loss, appetite altering and psychiatric medications
- Diagnosis of diabetes mellitus, hypertension, cancer, polycystic ovary syndrome, hypothyroidism, hyperthyroidism, infectious diseases (influenza, COVID-19, etc.), renal disease, dysgeusia, or gallbladder disease
- Weight loss $\geq 5\%$ of their body weight in the last 6 months
- Consumption of more than 20 g of alcohol per day
- Smoking
- Being pregnant or breastfeeding
- Being vegetarian or vegan

e. Exclusion criteria

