- Incomplete data and/or measurements
- Individuals that decide to leave the study

f. Sample size

The sample size was calculated using the formula for comparing two means with data previously reported by Douglas BR et al., who reported a significant difference ($p < 0.01$) in CCK concentrations when drinking 165 ml of regular coffee versus drinking 165 ml of NaCl water (16).

$$n = \frac{\sigma_1^2 + \sigma_2^2}{(x_1 - x_2)^2} (Z_{1-\alpha/2} + Z_{1-\beta})^2$$

n = sample size

$\alpha = 0.05$ $Z_{1-\alpha/2} = 1.96$

$\beta = 0.2$ $Z_{1-\beta} = 0.842$

x_1 = pmol/L of CCK when consuming regular coffee = 2.8

x_2 = pmol/L of CCK when consuming water containing NaCl = 0.4

σ_1 = standard deviation when consuming regular coffee = 2.2

σ_2 = standard deviation when consuming water containing NaCl = 0.2

Substituting these values in the formula, an “n” of 7 subject per intervention was obtained.

$$n = \frac{2.2^2 + 0.2^2}{(2.8 - 0.4)^2} (1.96 + 0.842)^2 = 7$$

In addition, as reported by Horner et al., the sample size to detect a 20 mm difference in visual analog scales to assess appetite between meals (post-breakfast - pre-breakfast) in a paired design with an $\alpha=0.05$ and a power of 80%, is 10 subjects (21).

g. Dependent and independent variables

Independent variable

- Coffee consumption

Dependent variables

- Hunger
- Satiety
- Ghrelin concentrations
- Cholecystokinin concentrations
- Dietary intake the day of the intervention

Confounding variables

- Score on the "Food restriction" section of the Three Factor Eating Questionnaire.
- Usual dietary Intake

h. Biosafety considerations

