
Three-factor eating questionnaire

This questionnaire consists of 51 items and is applied in the first session to assesses three dimensions of eating behavior: a) dietary restraint, consisting of 21 items intended to measure the cognitive dominance of food intake; b) disinhibition, containing 16 items assessing the tendency to overeat and loss of control overeating; and c) hunger susceptibility, with 14 items estimating subjective feelings of hunger and desire for food (33,34).

Breakfast

Participants will receive 2 breakfasts in two different sessions; one of them will consist of a breakfast that will include simple water as a beverage and in another session, they will have the same breakfast, but the beverage to be consumed will be coffee. The order in which the two types of beverages will be consumed will be random. Each breakfast will be offered 1 week apart and will consist of the following:

- Breakfast with coffee

1 cup of coffee with 6 mg/kg of body weight of caffeine and a breakfast with 400 kcal, with a distribution of 50% carbohydrates, 30% lipids and 20% protein.

A Veracruz coffee will be used, which according to a study carried out by the Federal Consumer Protection Agency (Profeco) reports that for every 7 grams of this coffee there are 111 mg of caffeine (35); once the participant's weight is obtained, a calculation will be made to know the amount in grams of coffee to be used; finally, the amount of coffee in 250 ml of water will be prepared. Likewise, before the intervention, tests will be carried out to see the tolerance to the taste.

- Breakfast without coffee

1 cup of simple water and a breakfast with 400 kcal, with a distribution of 50% carbohydrates, 30% lipids and 20% protein.

In the research carried out by Gavrieli et al. (3,4) and in a study by Beaudoin M et al. (36), simple water was used as a control beverage to analyze the effect of coffee on appetite regulating hormones. Based on this, it was decided to use simple swater as the control beverage for this study to make comparisons with the results obtained in other investigations.

Statistical analysis

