For descriptive statistics, quantitative variables will be expressed as mean \pm standard deviation or median and interquartile range, and qualitative variables as frequency or percentage. For inferential statistics, the distribution of the variables will first be analyzed with the Shapiro-Wilk test. In the event that the variable is not normally distributed, a logarithmic transformation will be

made, and it will be checked again if it is normally distributed; in the event that the variable continues with a non-normal distribution, non-parametric statistical tests will be used. For comparisons between the two treatments, the mixed general linear model will be used. The data will be entered into an Excel spreadsheet to later be imported into the SPSS v.21 program for analysis, considering a value of $p < 0.05$ as statistically significant. The graphs will be made with the Gradhpad software version 9.3.1.

10. Project viability

a. Funding

Financial resources are available to cover the expenses necessary to carry out the project, through the program "Support for the Incorporation of NPTC", report number 511-6/2020-8586 and through the PRO-SNI 2021 fund.

b. Infrastructure

Access to INNUGET of the University Center of Health Sciences of the Universidad de Guadalajara is available, which has all the necessary equipment to carry out this project.

11. References

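### The CCK sample size of 7 rests on normal quantiles; under normality a paired t-test on 7 women has about 67% to 75% power, while the 10 cited in the same section suffice

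*Combined protocol and SAP*

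**What the plan says.** Section 8.f opens: "The sample size was calculated using the formula for comparing two means with data previously reported". The inputs are two-sided alpha 0.05 (z = 1.96), beta 0.2 (z = 0.842), mean CCK of 2.8 pmol/L after coffee and 0.4 pmol/L after salt water, and SDs of 2.2 and 0.2. The result is an n "of 7 subject per intervention was obtained".

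The section then cites a second figure from another published study, for a 20 mm difference on the visual analogue scales (VAS) in a paired design: the number needed, at alpha 0.05 "and a power of 80%, is 10 subjects". It does not say whether 7 or 10 is the target, and it gives neither a within-woman correlation nor a dropout allowance.

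On design, section 8.a reads "Randomized crossover clinical trial", and section 9 (Breakfast) adds: "Participants will receive 2 breakfasts in two different sessions". Section 8.e lists incomplete data and leaving the study as grounds for exclusion. On analysis, section 9 (Statistical analysis) states: "For comparisons between the two treatments, the mixed general linear model will be used". The model's terms are not listed. The same paragraph provides for a log transformation, and then non-parametric tests, when a variable fails a normality check.

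**The concern.** A sample size formula with normal quantiles is accurate when the SD is well estimated. With 7 women each taking both drinks there are 7 differences and 6 degrees of freedom. The two-sided 5% critical value is then 2.447, not 1.96, so a formula that ignores this overstates power.

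CCK appears in the hypothesis and in specific objectives 3 and 5. A reader who takes 7 as enough believes the chance of missing the assumed effect is one in five. With normal data, an estimated SD and zero correlation it is about one in three. Because section 8.e excludes incomplete cases, any n that is meant to deliver the stated power has to be a number of completers.

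**Working it through.** **Inputs (all from section 8.f).** Means 2.8 and 0.4, so the difference is 2.4. SDs 2.2 and 0.2, so the sum of variances is 4.84 + 0.04 = 4.88. Two-sided alpha 0.05, power 80%. The within-woman correlation rho is not given, so it is varied from 0 to 1.

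**Step 1: the plan's figure.** n = 4.88 / 2.4² × (1.96 + 0.842)² = 4.88 / 5.76 × 7.851 = 6.65, rounded up to 7. The plan's figure reproduces. On the same basis, power at exactly n = 7 is Φ(2.4 × √7 / 2.209 − 1.96) = Φ(2.874 − 1.96) = 82%.

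**Step 2: paired t-test with the SD estimated.** The SD of a difference is √(4.88 − 2 × rho × 2.2 × 0.2) = √(4.88 − 0.88 × rho). This gives 2.209, 2.107 and 2.000 at rho 0, 0.5 and 1. The noncentrality parameter is 2.4 × √n / SD, and power comes from the noncentral t with n − 1 degrees of freedom. A period term costs one more degree of freedom (n − 2, balanced sequences).

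| Completers | rho 0 | rho 0.5 | rho 1 | rho 0, with period term |
|---|---|---|---|---|
| 7 | 67.1% | 71.0% | 75.4% | 63.6% |
| 9 | 81.4% | 84.8% | 88.2% | 79.8% |
| 10 | 86.3% | 89.2% | 92.0% | 85.2% |

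Simulation with 400,000 normal trials agrees: 67.2% (n = 7, rho 0), 75.4% (n = 7, rho 1) and 86.2% (n = 10, rho 0). Correlation does not rescue n = 7. The SDs are so unequal that even rho = 1 reduces the SD of the difference only from 2.209 to 2.000.

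**Step 3: t-quantiles in the plan's formula (rho 0).** At 6 degrees of freedom, 4.88 / 5.76 × (2.447 + 0.906)² = 9.52. At 8 degrees of freedom, 4.88 / 5.76 × (2.306 + 0.889)² = 8.65. The result settles at 9, but the table shows that 9 falls just under 80% at rho 0 once a period term is fitted.

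**Step 4: other readings of 7.**
- Two independent groups of 7: 67% by the Welch test. The pooled t-test gives 75%, but its type I error with these SDs is 7.1%.
- 7 per sequence, so 14 women: 96% at rho 0. There is no shortfall.

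**Step 5: dependence on normality.** A normal coffee arm with mean 2.8 and SD 2.2 would put Φ(−2.8 / 2.2) = 10% of concentrations below zero, so normality is doubtful for these inputs. As an assumption that the documents do not make, take positive distributions with the same means and SDs, rho 0 and n = 7, and simulate the paired t-test:

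| Distribution | Untransformed | Log scale |
|---|---|---|
| Gamma | 81% | 92% |
| Lognormal | 88% | 99.7% |

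**The case against.** The strongest reply is that the section already contains the remedy. The sentence after the derivation cites 10 subjects in a paired design, and 10 completers give at least 85% for CCK at any non-negative correlation, even with a period term. Nothing names 7 as the enrolment target. This stands, and it is why the point is minor. What remains is that the 10 is cited only for the VAS, and the section never says that it governs.

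Second, the shortfall is shown for a normal paired t-test, whereas the plan specifies a mixed model with unlisted terms and also says: "In the event that the variable is not normally distributed, a logarithmic transformation will be" made. This stands as well. With skewed positive data the planned route could reach or exceed 80% with 7 women, so the 67% to 75% must always carry its normality condition. The 6 degrees of freedom are likewise an inference from 7 women in a crossover, not a figure in the plan.

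A reader might also infer three stronger claims that the documents do not support:
- *The formula was miscalculated, or 67% is the power under its own model.* The substitution is right. The formula treats the SDs as known, and on that basis power at 7 is 82%. The 67% arises only when the SD is estimated.
- *The trial is underpowered for CCK.* That needs 7 women as the target together with normal data. The documents establish neither, and 7 per sequence would give 96%.
- *Nine would be enough.* Only without a period term, at rho 0.

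**Conclusion.** The point holds in a limited form. The 7 is computed correctly, but from an approximation that is too optimistic at this size. For 7 women in the crossover, with normal differences and the plan's means and SDs, power is about 67% at rho 0, 71% at rho 0.5 and at most 75% at rho 1, against the 80% intended. With a period term it is 64% at rho 0.

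This rests on three conditions: 7 means women rather than women per sequence, the differences are normal, and CCK is analysed untransformed. Under the same conditions the 10 already cited give 86% at rho 0. These figures take the published CCK inputs as given and do not test whether they suit this trial.

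Severity is minor: the consequence arises only if 7 is used as the target.

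**What to change.** In section 8.f, replace the statement based on normal quantiles with one based on t, for example: *Assuming normally distributed differences and the quoted inputs, a two-sided 5% paired t-test has about 67% power with 7 completers and 86% with 10 at within-woman correlation 0 (85% with 10 if a period term is fitted).*

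Then state that the target is 10 completers, the number already cited for the VAS, and not 7. Do not present 9 as sufficient.

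The cost is two sentences, and the stated CCK power at 7 becomes less favourable. The target does not rise above the 10 already cited. However, because section 8.e removes incomplete cases and leavers, securing 10 completers may mean enrolling somewhat more than 10. The section should state the dropout allowance it adopts; the documents give no rate from which to set one here.

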In the first session, participants will receive instructions on how to fill out the dietary record format to evaluate the individuals' diet, they are asked to record all food and beverages consumed during a 3-day period, being a weekday, a weekend day and the day prior to their second session. Nutritionist Pro™ Diet Analysis software (Axxya Systems, Stafford, TX, USA) is used for diet analysis.

Frequency of consumption of foods with caffeine

A search of the nutritional information of foods and beverages with coffee and/or caffeine most consumed in Mexico was made in the food databases, the magazine "Revista del Consumidor", a publication of the Mexican government, and in other sources where that information was available. This information was used to design a coffee and caffeine products frequency products and will be applied in each of the sessions to the participants.

Questionnaires

Clinical history

A clinical history will be taken during the first session to obtain information on pathological history, clinical data, nutritional aspects, sociodemographic and lifestyle aspects.

Visual analog scales

This evaluation format, which was previously reproduced and adapted to Spanish by our research group (manuscript in preparation), consists of questions that are asked before and after consuming breakfast, and subsequently at certain time intervals. The visual analog scales are composed of lines, usually 100 mm long, on which at one end is placed the term "None" or "Not at all" and at the other end the term "Yes, a lot" or "As much as I have never felt". The patient marks a point between these two extremes and quantification is done by measuring the distance from the left end of the line to the mark to which a score is given (31).

Physical Activity Questionnaire (IPAQ) short version

This instrument is a physical activity assessment format, that examines different dimensions of patient physical activity, such as time spent in walking, moderate and vigorous intensity activities

and time spending in sedentary activities. Weekly physical activity is measured by recording in METs (metabolic equivalent of task) per min per week. After calculating the physical activity index, whose value corresponds to the product of the intensity (in METs) times the frequency times the duration of the activity. The subjects are classified into 3 categories of high, moderate, and low physical activity (32). This questionnaire will be applied in the second and third sessions.

Three-factor eating questionnaire

This questionnaire consists of 51 items and is applied in the first session to assesses three dimensions of eating behavior: a) dietary restraint, consisting of 21 items intended to measure the cognitive dominance of food intake; b) disinhibition, containing 16 items assessing the tendency to overeat and loss of control overeating; and c) hunger susceptibility, with 14 items estimating subjective feelings of hunger and desire for food (33,34).

Breakfast

Participants will receive 2 breakfasts in two different sessions; one of them will consist of a breakfast that will include simple water as a beverage and in another session, they will have the same breakfast, but the beverage to be consumed will be coffee. The order in which the two types of beverages will be consumed will be random. Each breakfast will be offered 1 week apart and will consist of the following:

- Breakfast with coffee

1 cup of coffee with 6 mg/kg of body weight of caffeine and a breakfast with 400 kcal, with a distribution of 50% carbohydrates, 30% lipids and 20% protein.

A Veracruz coffee will be used, which according to a study carried out by the Federal Consumer Protection Agency (Profeco) reports that for every 7 grams of this coffee there are 111 mg of caffeine (35); once the participant's weight is obtained, a calculation will be made to know the amount in grams of coffee to be used; finally, the amount of coffee in 250 ml of water will be prepared. Likewise, before the intervention, tests will be carried out to see the tolerance to the taste.

- Breakfast without coffee

1 cup of simple water and a breakfast with 400 kcal, with a distribution of 50% carbohydrates, 30% lipids and 20% protein.

In the research carried out by Gavrieli et al. (3,4) and in a study by Beaudoin M et al. (36), simple water was used as a control beverage to analyze the effect of coffee on appetite regulating hormones. Based on this, it was decided to use simple swater as the control beverage for this study to make comparisons with the results obtained in other investigations.

Statistical analysis

For descriptive statistics, quantitative variables will be expressed as mean \pm standard deviation or median and interquartile range, and qualitative variables as frequency or percentage. For inferential statistics, the distribution of the variables will first be analyzed with the Shapiro-Wilk test. In the event that the variable is not normally distributed, a logarithmic transformation will be

made, and it will be checked again if it is normally distributed; in the event that the variable continues with a non-normal distribution, non-parametric statistical tests will be used. For comparisons between the two treatments, the mixed general linear model will be used. The data will be entered into an Excel spreadsheet to later be imported into the SPSS v.21 program for analysis, considering a value of $p < 0.05$ as statistically significant. The graphs will be made with the Gradhpad software version 9.3.1.

10. Project viability

a. Funding

Financial resources are available to cover the expenses necessary to carry out the project, through the program "Support for the Incorporation of NPTC", report number 511-6/2020-8586 and through the PRO-SNI 2021 fund.

b. Infrastructure

Access to INNUGET of the University Center of Health Sciences of the Universidad de Guadalajara is available, which has all the necessary equipment to carry out this project.

11. References

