Adult women between 25 and 40 years of age will be invited to participate in this study through social networks and personal invitations. Participants who meet the inclusion criteria and agree to participate will sign the informed consent form. Their participation involves their attendance to 3 sessions with a difference of one week between one and another. In the first session, they will be evaluated to determine whether or not they meet the inclusion criteria and will then be randomly assigned to the two types of interventions in the two subsequent sessions.

Anthropometry and blood pressure

Weight

Weight measurement is performed in the morning, after a period of 8 to 12 hours of fasting, with light clothing and with bare feet. An InBody model 370 electrical bioimpedance device with an accuracy of 0.1 kg is used. The subject is placed in the center of the scale without support and with his/her weight equally distributed on both feet.

Size

The size measurement is made with a Seca stadiometer which has an accuracy of 0.1 cm. The subject stands with feet together (heels together and toes slightly apart). The heels, buttocks, upper back, and occipital are in contact with the stadiometer. The head is placed in the Frankfort plane, without touching the equipment. The subject is instructed to take a deep, sustained breath in. To make the measurement, the square is placed firmly on the highest point of the skull, compressing the hair as much as possible. The measurement is taken at the end of a deep breath.

Waist circumference

Waist circumference measurement is performed with a Lufkin anthropometric tape, which has an accuracy of 1 mm. The subject keeps the arms crossed on the thorax, heels together with the toes a little apart and the view in the Frankfort plane. The measurement is taken at the narrowest level, between the edge of the lower costal (tenth rib) and the iliac crest. The subject breathes normally, and the measurement is taken at the end of an exhalation.

Hip circumference

Hip circumference measurement is performed with the same Lufkin brand tape and in the same position as described for waist circumference. The circumference is taken at the maximum posterior level of the buttock bulge.

Electrical bioimpedance

The measurements of fat mass, fat percentage, fat-free mass and bone mass are obtained through the InBody 370 equipment, under the same conditions described for the measurement of body weight.

Blood Pressure

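### Food intake is recorded the day before session 2 but not the day before session 3, and nothing matches the two days; this mainly costs precision in a small crossover and is cheap to put right

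*Combined protocol and SAP*

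**What the plan says.** Section 9 (Selection of participants) plans "attendance to 3 sessions with a difference of one week between one and another". Session 1 is for screening, and the two beverages are given in sessions 2 and 3. Under Breakfast, "The order in which the two types of beverages will be consumed will be random" and "Each breakfast will be offered 1 week apart".

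Under Dietary Record, "In the first session, participants will receive instructions on how to fill out the dietary record format". The three days are described as "being a weekday, a weekend day and the day prior to their second session". The day before session 3 is not among them.

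Section 8.g lists two confounding variables: usual dietary intake, and the restraint score, which is the food-restriction "section of the Three Factor Eating Questionnaire". Section 9 says of that instrument: "This questionnaire consists of 51 items and is applied in the first session".

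Three other features bear on the point. Blood in sessions 2 and 3 is drawn after an 8 to 12 hour fast. A frequency questionnaire on caffeine products is given at every session. Appetite and hormones are measured at t=-30 and t=0 as well as later, and specific objectives 4 and 5 compare the change from t=0 to t=180. The Statistical analysis section names a mixed general linear model, with no covariates and no period or sequence term.

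**The concern.** In a two-period crossover each woman is her own control, so the beverage contrast is disturbed only by things that differ between her two test sessions. What she ate and drank the day before is one of these. The plan captures it for one test session and not the other. It does not ask for the same intake to be repeated, for a standard evening meal, or for a caffeine limit on the day before.

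Two consequences follow. First, day-to-day differences in prior intake enter the coffee-minus-water difference as noise that can be neither reduced nor examined afterwards. With planning sizes of 7 and 10, chance imbalance in this noise can be noticeable. Second, women keep a diary before session 2 and not before session 3. If diary-keeping alters eating, that is an avoidable difference between periods.

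The variables labelled as confounders in section 8.g do not help, because neither changes between a woman's two sessions.

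**Working it through.** **1. What is known about the day before each test session**

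| | Before session 2 | Before session 3 |
|---|---|---|
| Food record | Yes | No |
| Intake matched to the other session | No | No |
| Fast of 8 to 12 h | Yes | Yes |
| Caffeine-product frequency questionnaire at the session | Yes | Yes |
| Physical activity questionnaire at the session | Yes | Yes |

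The last two rows cover habitual caffeine sources and activity. Neither is a record of the previous day's food.

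**2. What cancels and what does not.** Write the outcome for woman i in session j as

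y_ij = u_i + γ·z_i + β·x_ij + τ·(coffee) + e_ij,

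where z_i is a per-woman value (restraint score, usual intake) and x_ij is previous-day intake. Her coffee-minus-water difference is

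τ + β·(x_coffee − x_water) + (e_coffee − e_water).

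The z_i term has gone. Section 8.e excludes women with incomplete data, so the analysed set is complete pairs and the cancellation is exact for main effects. The x term remains unless intake is matched or measured in both sessions.

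**3. The plan's own figures (section 8.f).** For CCK: (2.2² + 0.2²)/(2.8 − 0.4)² × (1.96 + 0.842)² = 6.65, rounded up to 7. This reproduces. The second figure, 10 women for a 20 mm paired difference on the visual analogue scale at 80% power, is cited without an SD and so cannot be reproduced. Solving backwards with a paired t-test (two-sided 0.05) gives SD = 20.1 mm for the paired difference; the normal approximation gives 22.6 mm.

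**4. Illustration.** The added SD s is an assumption, taken as independent of the 20.1 mm. The total SD is √(20.1² + s²). The 95% range for the chance shift in a 10-woman mean is ±1.96·s/√10.

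| Added SD s (mm) | Total SD (mm) | Power, n = 10 | n for 80% | Chance shift (mm) |
|---|---|---|---|---|
| 0 | 20.1 | 80% | 10 | – |
| 5 | 20.7 | 78% | 11 | ±3.1 |
| 10 | 22.4 | 71% | 12 | ±6.2 |

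**5. Noise or bias.** A simulation of 20,000 trials of 10 women, with intake varying at random between sessions (added SD 10 mm), raised the SD of the estimate from 6.3 to 7.1 mm. The mean shift stayed at about 0 (0.06 mm).

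**6. The diary difference.** Let δ be any session-3-minus-session-2 effect. With equal sequences it cancels from the beverage contrast. If order were assigned by simple randomisation to 10 women, the chance of a 7:3 or more uneven split is 2 × (1 + 10 + 45 + 120)/1024 = 352/1024 = 34%. At 7:3 the unadjusted estimate moves by (7 − 3)/10 × δ = 0.4δ in absolute size. A period term removes this. The plan states neither balanced sequences nor a period term. No value of δ can be taken from the documents.

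**The case against.** The strongest reply is that randomised order already deals with this. Previous-day intake is not systematically tied to beverage, so the contrast is unbiased in expectation. A reader might infer from the gap that the coffee-water comparison is confounded, and the documents do not support that: step 5 shows a wider estimate, not a shifted one. What remains is variance and chance imbalance, which randomisation does not remove.

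A second reply is that fasting measures and change scores absorb the effect. A shift that is the same at t=0 and t=180 drops out of objectives 4 and 5. This stands as partial cover only, because objectives 2 and 3 compare values at each time point.

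Third, the fast and the caffeine questionnaire are real controls, and the plan should be credited with them. Neither fixes or records the previous day's food.

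Fourth, the abstract speaks of food records in the plural, so a second record might be intended. The Dietary Record section is the operative text and describes one.

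Fifth, section 8.g only lists variables, and the model names no covariates. That is right. Including a per-woman score would not bias the contrast; it simply cannot adjust it. This part of the point is about labelling.

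Sixth, the cited n = 10 may already include ordinary day-to-day variation, in which case the power losses in step 4 are overstated. This stands, and those figures are illustrations for that reason.

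**Conclusion.** The gap is real: previous-day intake is recorded before one test session, is unrecorded before the other, and is matched for neither. Its main effect is avoidable within-woman variance and chance imbalance in a small trial. The diary difference matters only if keeping a diary changes intake, sequences end up unequal, and no period term is fitted.

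The size is unknown. The 78% and 71% power figures rest on three assumptions: an added SD of 5 or 10 mm, its independence from the rest of the variation, and an implied SD of about 20 mm that excludes it. A reader could reach a far larger figure by assuming a within-woman intake SD of 300 to 500 kcal and a slope of 0.5 to 2 mm per 100 kcal. That gives 2.1 to 14.1 mm, or 1% to 50% of the implied variance. The documents support none of those inputs, and a range that wide settles nothing. No figure can be offered for ghrelin or CCK.

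Systematic bias would need something more, such as women inferring their session 3 drink (coffee and water cannot be masked) and eating differently beforehand. Nothing in the documents shows this, though without a record it could not be detected. This is a worthwhile low-cost improvement; it does not invalidate the comparison.

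**What to change.** - Give each woman a copy of her record for the day before session 2, and ask her to repeat that food and drink on the day before session 3.
- Have her keep the same one-day record before session 3, so that both periods carry the same diary task.
- Report the between-session difference in previous-day intake. If it is material, use it as a session-level covariate, with period in the mixed model.
- In section 8.g, describe the restraint score and usual intake as descriptors or possible effect modifiers, not as confounders of the beverage contrast.

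The cost is one copied record and one extra diary day per woman, analysed in the diet software already in use, with no added visit. The limitation is that adherence to the repeated day is self-reported. The second record makes departures visible but does not verify them.
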